1373 **9.3.2 Adjustment for Baseline Characteristics**

1374 If clinically important differences are found between the groups at baseline, particularly with
1375 regard to important variables such as age, gender, race/ethnicity, or visual acuity, the primary
1376 outcome analyses will be repeated after statistically adjusting for these differences. These
1377 analyses will be considered secondary, however.

1378 **9.3.3 Investigation of Treatment by Covariate Interactions**

1379 We will investigate the interaction between treatment group and selected baseline covariates
1380 (age, race/ethnicity, PMD, papilledema grade, RNFL thickness, total retinal thickness, optic
1381 nerve head volume, visual acuity, presence of transient visual obscurations, and the symptom of
1382 constant visual loss) separately by adding the appropriate main effect and interaction terms to the
1383 primary statistical model and testing for significance of the interaction. Since the power to detect
1384 potentially meaningful interactions will be limited, the magnitudes of mean responses to
1385 treatment in the relevant subgroups will be examined. The observation of clinically important
1386 subgroup differences in mean treatment response will serve as hypothesis generation for possible
1387 future studies designed to address specifically the issue of differential therapeutic response.
1388 Although these analyses are purely exploratory, those involving papilledema grade, PMD, visual
1389 acuity, and race/ethnicity will be given higher priority.

1390 **9.3.4 Verification of Model Assumptions**

1391 The underlying assumptions of the statistical model to be used in the primary analysis will be
1392 thoroughly checked (e.g., linearity), and remedial measures (e.g., transformations) may be taken
1393 if serious violations of these assumptions are detected.

1394 **9.3.5 Treatment of Missing Data**

1395 Multiple imputation will be used to deal with missing data. This will be applied using a
1396 regression-based imputation model. For subjects with complete data up to a particular visit, a
1397 multiple regression model will be fit that includes the outcome at that visit as the dependent
1398 variable and outcomes at previous visits and treatment group as independent variables. Separate
1399 models will be similarly constructed for each visit (Weeks 1, 4, 8, 16, and 26). Using these
1400 regression models, a missing value for a subject at a particular visit will be imputed as a draw

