117 fairly strong correlation between the baseline and final PMD values ($r = 0.52$). When considering
118 only subjects who were followed for at least 5.5 months ($n = 56$), the correlation between the
119 baseline and final PMD values was actually somewhat higher ($r = 0.62$) and the residual standard
120 deviation in the analysis of covariance model was smaller (6.0 dB).

121 Assuming a standard deviation of 6.5 dB, and a Bonferroni-adjusted two-tailed significance level
122 of 1.7%, in order to detect a group difference assuming a true difference of 4.5 dB with 88%
123 power, a sample size of 54 subjects per group is required. The sample size will be inflated to 60
124 subjects per group (180 total) to accommodate an anticipated 10% rate of subject
125 withdrawal/dropout.

126 The assumed standard deviation of 6.5 dB was selected based on the calculated standard
127 deviation of the residuals from the above analysis of covariance model (6.3 dB) under the
128 following assumptions: 1) the distribution of baseline PMD in the study cohort will be similar to
129 that observed in the pilot study, and 2) the higher standard deviation observed in the pilot study
130 surgical groups can be attributed to the increased probability of those with worse PMD at
131 baseline to receive surgery (participants with worse PMD at baseline had higher variability of
132 change in PMD)^a. The power remains above 80% even if the assumed standard deviation is as
133 large as 7.1 dB.

134 The inclusion of the worst eligible eye is expected to increase power, but the increase is expected
135 to be small (approximately 3%) because the preliminary data from the chart review indicate that
136 only ~40% of subjects will contribute a second eligible eye to the analysis and the correlation
137 between the outcomes in the two eyes is quite high (0.82 in our sample). This assumes that the
138 group difference will be comparable in the best and worst eligible eyes, as we anticipate.

139 The chosen effect size of 4.5 dB is based on the following rationale. Visual field defects are
140 similar in IHH and glaucoma and data on the relationship between vision-specific quality of life
141 (as measured by the NEI-VFQ-25) and PMD from the better seeing eye are available from 213
142 subjects with glaucoma in the Los Angeles Latino Eye Study. A regression analysis yielded the
143 finding that a change of 1 dB in PMD corresponded to an approximately one-unit score change

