180 • There are no abnormalities on ophthalmoscopy or fundus photos
181 related to myopia that are associated with visual loss (such as
182 staphyloma, retinal thinning in the posterior pole, or more than
183 mild optic disc tilt), and

184 • The individual will wear a contact lens for all perimetry
185 examinations with the appropriate correction

186 ▪ Eyes with more than 6.00D of hyperopia but less than 8.00D of hyperopia
187 are eligible if:

188 • There is an unambiguous characteristic halo of peripapillary edema
189 as opposed to features of a small crowded disc or other hyperopic
190 change related to visual loss determined by the Site Investigator or
191 the PRC Director (or his designate), and

192 • The individual will wear a contact lens for all perimetry
193 examinations with the appropriate correction (which can be
194 corrected for perimetry or the patient's own contact lens with over
195 correction by lens at perimeter)

196 ○ Other disorders causing visual loss except for refractive error and amblyopia,
197 including cells in the vitreous or iritis

198 ○ Large optic disc drusen on exam or in previous history (small drusen of the disc
199 can occur with longstanding papilledema and are allowed if not so numerous that
200 investigator determines they are contributing to vision loss).

201
 202 Every effort will be made to retain subjects in this study, to promote adherence to the study
 203 protocol, and to collect all data at every visit. If a subject cannot tolerate study medication or
 204 refuses to receive the study intervention, we will continue to follow and evaluate that subject if
 205 he/she is willing. If a subject drops out, attempts will be made to bring the subject back for a
 206 final evaluation. Compliance with trial procedures, drop-outs/drop-ins, and reasons for subject
 207 withdrawal will be carefully tracked throughout the study.

208
 209 **3.2 Analysis of the Primary Outcome Variable**

210 **3.2.1 Definition of Primary Outcome**

211 The primary outcome variable will be the change from baseline to first of Month 6 or time of
 212 treatment failure in PMD in an eligible eye, with data from all eligible eyes included in the
 213 primary analysis (refer to the table below for a description of eyes included in the primary
 214 analysis).

215

Eyes at baseline	Eyes included in primary analysis
No eligible eyes → subject not eligible	None (subject not eligible)

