273 mean responses to treatment in the relevant subgroups will be examined. The observation of
274 clinically important subgroup differences in mean treatment response will serve as hypothesis
275 generation for possible future studies designed to address specifically the issue of differential
276 therapeutic response. Although these analyses are purely exploratory, those involving
277 papilledema grade, PMD, visual acuity, and race/ethnicity will be given higher priority.

278 Interpretation of subgroup analyses should be viewed with caution, irrespective of whether the
279 overall analysis demonstrates a significant treatment group difference. Extreme caution is
280 particularly needed in the absence of such an overall difference.

281

282 **3.2.5 Verification of Model Assumptions**

283 The underlying assumptions of the statistical model to be used in the primary analysis will be
284 thoroughly checked (e.g., linearity) through assessment of scatterplots of change in PMD versus
285 baseline PMD within treatment group, and remedial measures (e.g., inclusion of baseline PMD
286 categorized according to randomization strata) may be taken if serious violations of these
287 assumptions are detected.

288

289 **3.2.6 Treatment of Missing Data**

290 Multiple imputation will be used to deal with missing data. This will be applied using a
291 regression-based imputation model. For subjects with complete data up to a particular visit, a
292 linear regression model (identity link) will be fit that includes the outcome at that visit as the
293 dependent variable and outcomes at previous visits and treatment group as independent
294 variables. Separate models will be similarly constructed for each visit (Weeks 4, 8, 16, and 26).
295 Using these regression models, a missing value for a subject at a particular visit will be imputed
296 as a draw from the predictive distribution given the outcomes at previous visits (some possibly
297 imputed) and treatment group. This will be done sequentially starting with the Week 4 visit and
298 ending with the Week 26 (Month 6) visit. This process will be repeated 100 times, resulting in
299 100 complete analysis data sets. The analyses (Section 3.2.2) will be performed separately for
300 each of the 100 complete analysis data sets, and the results will be combined into one multiple
301 imputation inference (estimated treatment effect and associated confidence interval and p-value)

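### SAP 3.2.6 should say that baseline PMD enters every imputation regression; read literally it does not, which can bias the adjusted difference when drop-out severity differs between arms

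*SAP*

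**What the plan says.** SAP 3.2.6 specifies sequential regression imputation with 100 data sets, combined by Rubin's rules and justified under missing at random. Each regression has the outcome at a visit as the "dependent variable and outcomes at previous visits and treatment group as independent" variables. On timing it says: "Separate models will be similarly constructed for each visit (Weeks 4, 8, 16, and 26"). Nothing else is listed as a predictor.

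Three other places bear on this:

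- **Outcome definition.** SAP 3.2.1 begins: "The primary outcome variable will be the change from baseline to first of Month 6 or time of" treatment failure, in PMD. The same section also uses the word outcome for a PMD level, when it distinguishes baseline PMD from outcome PMD.
- **Analysis model.** SAP 3.2.2 fits an ANCOVA by GEE with treatment group and baseline PMD. Protocol 3.2 stratifies randomization by PMD.
- **Protocol version of the imputation.** Protocol 9.3.5 has the same predictors but a different start: "models will be similarly constructed for each visit (Weeks 1, 4, 8, 16, and 26"). Size V perimetry is performed at the Week 1 and Week 2 safety visits (Protocol 5.1.5).

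SAP 3.3.6 applies the method of 3.2.6 to the continuous secondary outcomes at Month 6. SAP 3.3.2 adjusts those for their own baseline value.

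**The concern.** Missing at random is a claim conditional on the variables in the imputation model. If the analysis adjusts for baseline PMD and the imputation ignores it, every subject missing from Week 4 onward in a given arm is imputed from the same distribution of change, however damaged the eye was at entry. In the pilot data, worse eyes changed more. An arm that loses its worse eyes would then have imputed improvements that are too small for those eyes, and its adjusted mean would be pulled down.

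This concerns the prespecified primary analysis, and the missing variable costs nothing: an eye cannot be randomized without a baseline PMD confirmed by the reading center. The same wording reaches CSF pressure, VFQ-25, SF-36 and HIT-6. Within the six-month trial these are measured only at baseline and Week 26, and the Week 26 lumbar puncture is voluntary. Read literally, they would be imputed from treatment group alone.

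**Working it through.** **1. The plan's own figures.** For 88% SAP 2.0 states: "power, a sample size of 54 subjects per group is required. The sample size will be inflated to 60" per group, with SD 6.5 dB, difference 4.5 dB and two-sided 1.7%. Check: SE = 6.5 × √(2/54) = 1.251; 4.5/1.251 = 3.597; critical value 2.387; power = Φ(3.597 − 2.387) = Φ(1.210) = 0.887. Inflation: 54/(1 − 0.10) = 60. Both reproduce. For scale, at 60 per group the SE of a pairwise difference is 6.5 × √(2/60) = 1.19 dB. The documents give no figure for the imputation model itself.

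**2. Slope of change on baseline PMD.** The documents do not state it, and their pilot figures support a range.

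- *Low end.* Slope = r × SD(final)/SD(baseline) − 1, with r = 0.52 (Protocol 9.10) and the SDs in Protocol Table 1. Medical: 0.52 × 9.2/6.2 − 1 = −0.23. ONSF: 0.52 × 9.0/7.1 − 1 = −0.34. Shunt: 0.52 × 8.4/6.2 − 1 = −0.30.
- *High end, from the residual SD.* Pooled within-group variance of change (SDs 6.9, 8.9, 8.0; n = 43, 24, 24) = (42 × 6.9² + 23 × 8.9² + 23 × 8.0²)/88 = 60.2. Pooled baseline variance (Table 1, same n) = (42 × 6.2² + 23 × 7.1² + 23 × 6.2²)/88 = 41.6. Slope = −√((60.2 − 6.3²)/41.6) = −0.70.
- *High end, from the VPS shift.* The raw VPS-minus-medical difference is 8.2 − 5.5 = 2.7 dB and the adjusted one is 1.13 dB. The baseline gap in Table 1 is −17.0 − (−14.6) = −2.4 dB. Slope = (2.7 − 1.13)/(−2.4) = −0.65.

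Table 1 and section 9.10 give slightly different pilot summaries, so neither end is exact.

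**3. Bias by hand, loss before Week 4, literal model.** Suppose one arm loses a share p selectively and the other loses at random. The selective arm is in effect assigned its completers' mean change, so

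bias = p × |slope| × (baseline gap between completers and drop-outs),

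acting against the arm with the selective loss. Assume baseline PMD is uniform from −27 to −6 dB (mean −16.5) and p = 0.10.

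- *Drop-outs drawn from the worse half:* mean −21.75. Completers: (−16.5 + 0.10 × 21.75)/0.90 = −15.92. Gap 5.83 dB.
- *Drop-outs are the worst tenth:* mean −25.95. Completers: (−16.5 + 0.10 × 25.95)/0.90 = −15.45. Gap 10.5 dB.

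| Slope | Worse half | Worst tenth |
|---|---|---|
| −0.23 | 0.13 dB | 0.24 dB |
| −0.34 | 0.20 dB | 0.36 dB |
| −0.65 | 0.38 dB | 0.68 dB |
| −0.70 | 0.41 dB | 0.74 dB |

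If both arms lose the same share with the same gap, the two terms cancel and the bias is zero.

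**4. Simulation check.** Two arms of 300,000, one eye each, true difference 0. Assumptions: slope −0.30 to −0.65, residual SD 6.5 dB, adjacent-visit residual correlation 0.75, 10% drop-out. Absolute bias in dB:

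| Drop-out pattern | Literal SAP, lost before Week 4 | Literal SAP, lost after Week 8 | Baseline PMD added |
|---|---|---|---|
| Equally worse in both arms | about 0 | about 0 | about 0 |
| Worse baseline in one arm, random in the other | 0.20 to 0.71 | 0.10 to 0.27 | about 0 |
| Opposite severity in the two arms | 0.46 to 1.34 | 0.23 to 0.58 | about 0 |

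About 0 means within 0.05 dB. At 20% drop-out the second row becomes 0.46 to 1.36 dB before Week 4 and 0.23 to 0.51 dB after Week 8. The completers-only ANCOVA is also about 0 in all three rows.

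**5. Effect on the test.** With SE 1.19 dB, final boundary Z = 2.400 and a normal approximation, a bias of 0.2 dB moves the nominal 0.0164 to about 0.018, and 0.7 dB moves it to about 0.037.

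**6. Early fields.** If one arm loses subjects with a poor Week 1 field before Week 4 (10% drop-out), the bias is 0.45 to 0.61 dB under the literal model. It is 0.34 to 0.40 dB with baseline PMD alone added, about the same for completers-only, and about 0 once the Week 1 field is used.

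**The case against.** The strongest answer is that the omission is inferred. SAP 3.2.6 does not say that the imputed quantity is a change. SAP 3.2.1 also uses outcome for a PMD level, and SAP 1.0 lists a baseline visit. If PMD is imputed and baseline counts as a previous visit, the Week 4 model already contains baseline PMD and the bias disappears. That reading also gives the phrase about previous visits some content at Week 4, which the literal reading does not. This stands. A reader might infer that the SAP definitely excludes baseline PMD; the text supports only that it does not name it.

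A reader might also infer that any difference in severity between drop-outs and completers biases the contrast. It does not: equal selection in all arms cancels.

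The larger figures need the steep slope, strong selection in one arm and loss before Week 4 of the whole planned 10%. The plan works against that. Early treatment failures keep an observed outcome, the Month 6 window is wide (168 to 242 days), and withdrawing subjects are asked back for a final visit. SAP 3.2.7 also repeats the ANCOVA without participants lacking outcome PMD. That repeat still adjusts for baseline and is nearly unbiased when loss depends on baseline and arm, though not when it follows a poor early field. It therefore tempers the concern, but it leaves a primary analysis that could do worse than its own sensitivity analysis.

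Finally, the absence of Week 1 from the SAP might be taken as an error in itself. The documents do not support that. Safety visits are timed from randomization in the medical arm but from each operation in the surgical arms, and their schedule may be modified (Protocol 5.1.2). Leaving them out of a model indexed by visit is defensible. What remains is that the two documents disagree and the SAP gives no reason.

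**Conclusion.** The point holds as an unresolved specification with a possible bias under its literal reading. It is not a demonstrated bias in the trial. SAP 3.2.6 should not leave open whether the sole covariate of the primary ANCOVA is in the imputation model.

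On the literal reading, with 10% drop-out before Week 4 and worse-baseline loss in one arm only, the bias is roughly 0.1 to 0.7 dB. It is about 0.1 to 0.3 dB when loss follows Week 8. That compares with a pairwise SE of about 1.2 dB and a design difference of 4.5 dB. These sizes rest on assumptions that the documents do not give: a slope between about −0.25 and −0.7, a uniform baseline distribution, the strength of selection and the correlation between visits. Without a between-arm difference in drop-out severity, the bias is nil. This is a free improvement.

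**What to change.** In SAP 3.2.6:

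- State that PMD is the quantity imputed at each visit.
- Include baseline PMD and treatment group in every imputation regression, together with PMD at the earlier visits.
- Derive change from baseline after imputation.

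In SAP 3.3.6, state that the baseline value of each continuous secondary outcome enters its imputation model.

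Reconcile the Week 1 start in Protocol 9.3.5 with the Week 4 start in the SAP, and give the reason for the choice. Using the safety-visit fields is optional: they protect against loss that follows a poor early field, but their timing differs by arm.

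The cost is SAP wording, plus a conforming edit to the Protocol if Week 4 is kept. No new data, visits or sample size are needed.

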634 stimulus size III may be performed prior to two size V tests if a recent size III result is not
635 available. The size III test can be used as a guide as to whether the subject is likely to have at
636 least one eye meet eligibility criteria when size V testing is done.

637 • PMD using the size III stimulus should be approximately in range of -8.5 to -30 dB.

638 Two size V stimulus fields will be performed in each eye.

639 • The two size V stimulus visual field examinations will be transmitted to the Visual Field
640 Reading Center which will evaluate the visual field results: In order for an eye to qualify
641 for the trial, the average PMD with stimulus size V will have to be equal to or worse than
642 -6 dB and better than -27 dB.

643 • If the Visual Field Reading Center confirms that the subject is eligible for randomization,
644 it will document the average mean deviation of the two size V tests as well as which eyes
645 qualify as eligible eyes.

646 • If the Visual Field Reading Center finds performance issues on the perimetry results, the
647 examination will need to be repeated for the subject to be considered for the randomized
648 trial.

649 *Depending on the subject's condition (e.g., suspected visual deterioration, fatigue), perimetry*
650 *may be repeated later that day, or up to the 3-day deadline for randomization; the only exception*
651 *being if a perimetry result is unreliable and requires a repeat examination, the site will have an*
652 *additional two working days to complete the visual field examination. These additional sets of*
653 *perimetry examinations will be submitted to the Visual Field Reading Center for*
654 *confirmation/denial of eligibility.*

655 There will be times that perimetry results are not reliable and a repeat examination will be
656 necessary. This may occur not only at the screening/baseline visit but also at any visit. Whenever
657 two examinations are required (baseline, 6 months, treatment failure protocol) the following
658 outcomes are possible:

659 1. Two examinations performed and: (1) performance criteria are met and (2)
660 pathophysiologic appropriate visual field patterns match. The average of the mean
661 deviations is used for the outcome. Acceptable performance criteria are: the false positive
662 rate is less than 15%, the false negative rate is judged not to be excessive for the amount
663 of visual loss, and gaze tracking data confirms acceptable fixation. All data from eyes in

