One eligible eye and non-eligible eye too good	One eye that was eligible at baseline, regardless of what happened to either eye during study
One eligible eye and non-eligible eye too bad	One eye that was eligible at baseline, regardless of what happened to either eye during study
Two eligible eyes	Both eyes that were eligible at baseline, regardless of what happened to either eye during study

216
 217
 218 Treatment of subjects who have reached criteria for treatment failure will be at the discretion of
 219 the Site Investigator, and this treatment may yield a different outcome than randomized
 220 treatment. For this reason, the primary outcome variable for subjects who reach criteria for
 221 treatment failure prior to Month 6 will be the PMD measured at the time of treatment failure for
 222 purposes of the primary analysis. It is anticipated that no more than 15% of subjects will reach
 223 criteria for treatment failure prior to Month 6.
 224

225 PMD (baseline or outcome) will be the average PMD from the two reliable visual field
226 examinations (i.e. meeting Visual Field Reading Center criteria) performed at the visit; if only
227 one reliable result is obtained on the visual field examination, the one reliable result will be
228 analyzed; if a reliable result is not obtained on the visual field examinations, the PMD will be
229 considered missing.

230

231 Outcome PMD (excluding PMD at time of treatment failure) from visual field testing performed
232 out of the window of 168-242 days from randomization will be considered missing for the
233 primary analysis. Note this means a subject can be up to two weeks early and up to a full 60
234 days late, this latter choice was made with clinician input that they would rather have a
235 measurement than impute.

236

237 **3.2.2 Primary Statistical Model**

238 The primary statistical analysis will involve fitting an analysis of covariance model using
239 generalized estimating equations (GEE) with treatment group as the factor of interest and
240 baseline PMD as a covariate. These analyses will accommodate correlation among the within-
241 subject responses between the two eyes; an exchangeable working correlation structure will be
242 used. Standard errors for the model parameters will be estimated using the robust “sandwich”
243 estimators. The model also does not rely on the assumption of normality.

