- 340 • Change from baseline to Month 6 (pre-lumbar puncture) in optic nerve head volume
- 341 • Change from baseline to Month 6 (pre-lumbar puncture) in ganglion cell layer thickness

- 342 • Change from baseline to Month 6 (pre-lumbar puncture) in optic nerve canal shape
- 343 • Change from baseline to Month 6 in ETDRS visual acuity score
- 344 • Change from baseline to Month 6 in SF-36v2 scores
 - 345 ○ Change will be calculated separately for each of the eight health domains and the
 - 346 physical component summary (PCS) and mental component summary (MCS)
 - 347 scores
 - 348 ○ Scores determined via SF-36v2 scoring software
- 349 • Change from baseline to Month 6 in VFQ-25 score
 - 350 ○ Score determined as an average of sub-scale scores as described in the VFQ-25
 - 351 manual ([..\References\Participant Questionnaires\VFQ25_Manual.pdf](#))
 - 352 ▪ Scoring of missing items will follow the scoring instrument
- 353 • Change from baseline to Month 6 in VFQ-25 Neuro-Ophthalmic Supplement score
 - 354 ○ Score determined as described in the 10-item Neuro-Ophthalmic instructions
 - 355 ([..\References\Participant Questionnaires\Prior to Executed](#)
 - 356 [Agreement\10ItemNeuroOphthalVFQ25.pdf](#))
 - 357 ▪ Scoring of missing items will follow the scoring instrument
- 358 • Change from baseline to Month 6 in HIT-6
 - 359 ○ Score determined as a sum of scores for each question (Never = 6, Rarely = 8,
 - 360 Sometimes = 10, Very Often = 11, Always = 13; total score range 36 to 78 with
 - 361 higher score indicating greater life impact)
 - 362 ○ Surveys with ≥ 1 missing responses will be given an overall null score for the visit
- 363 • Change in headache severity from baseline to Month 6 as reported on the Headache
- 364 Assessment form
 - 365 ○ Analyzed as a continuous value with the following categories assigned for
 - 366 display:
 - 367 ▪ Mild = score 1-4 | Moderate = score 5-7 | Severe = score 8-10
- 368 • Month 6 VFRC determination of whether the visual field examination has improved,
- 369 remained the same, or worsened
 - 370 ○ All available visual field examinations will be analyzed. For the initial secondary
 - 371 outcome, the Month 6 VFRC rating will be used; a supplemental secondary
 - 372 outcome will use the VFRC rating at time of treatment failure for subjects
 - 373 experiencing treatment failure prior to Month 6.
- 374 • Change in weight from baseline to Month 6

375

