 376 Data from all eligible eyes will be included in the analysis. With the exception of CSF opening
 377 pressure and VFRC determination of visual field status, the outcomes also will be examined with
 378 change from baseline to Months 12, 24, 36.

379
 380 **3.3.2 Secondary Statistical Models**

381 Treatment effect on secondary outcome variables for efficacy that are continuous will be
382 analyzed using the same methods described in *Section 3.2.2* for the primary outcome variable,
383 except that a working correlation structure will not be needed for variables that are not eye-
384 specific. Variables to be analyzed in this manner are:

- 385 • Change in PMD at Month 6
- 386 • Change in CSF opening pressure (does not require working correlation structure)
- 387 • Change in papilledema grade (both reading center and study center outcomes)
- 388 • Change in RNFL thickness
- 389 • Change in total retinal thickness
- 390 • Change in optic nerve head volume
- 391 • Change in ganglion cell layer thickness
- 392 • Change in optic nerve canal shape
- 393 • Change in ETDRS visual acuity score
- 394 • Change in SF-36 scores (8 subscale domains, PCS and MCS; does not require working
395 correlation structure)
- 396 • Change in VFQ-25 score (does not require working correlation structure)
- 397 • Change in VFQ-25 Neuro-Ophthalmic Supplement score (does not require working
398 correlation structure)
- 399 • Change in HIT-6 (does not require working correlation structure)
- 400 • Change in headache severity as reported on Headache Assessment form (does not require
401 working correlation structure)
- 402 • Change in weight

403
404 The treatment effect on the ordinal outcome of Month 6 visual field examination status by
405 the VFRC (improved, no change, worse) will be assessed via a logistic regression model
406 (proportional odds model). A likelihood ratio test will be performed for significance of the
407 adjusted treatment group odds ratios representing pair-wise treatment group comparisons;
408 98.3% confidence intervals will be constructed for these odds ratios.

409
410 All models will include treatment group as the factor of interest and the baseline value of the
411 outcome variable as a covariate (to replace baseline PMD adjustment in the primary for
412 continuous outcomes; Month 6 visual field examination status by VFRC will retain inclusion
413 of baseline PMD).

415 **3.3.3 Adjustment for Baseline Covariates**

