- 594 • VPS completion status (VPS group)
- 595 • Surgical complications (separately for ONSF and VPS groups)
- 596 • Reoperations (ONSF)
- 597 • Shunt revisions (VPS)
- 598 • Headache by visit
- 599 • Weight by visit
- 600 • Visual field at follow-up (eligible eyes and non-eligible eyes, separately)
- 601 • Visual acuity at follow-up (eligible eyes and non-eligible eyes, separately)
- 602 • Papilledema grading at follow-up (eligible eyes and non-eligible eyes, separately)
- 603 • RNFL and macula GCL at follow-up (eligible eyes and non-eligible eyes, separately)
- 604 • Protocol deviations

605
606 Treatment Failure Identification Phase (Post 6-Month RCT)

- 607 • Adherence to medical management and diet by visit
- 608 • Daily dosage of acetazolamide and furosemide prescribed at each visit
- 609 • Medical therapy at each visit
- 610 • Protocol deviations.

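### The Month 6 visual field rating is modelled without any allowance for two eyes per subject, so its pairwise tests would run at about 3–4.5% instead of 1.67%

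*SAP*

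**What the plan says.** The rating (improved, no change, worse) is listed as a key secondary efficacy outcome in the Protocol Summary and is defined in SAP 3.3.1. There is a supplemental version that uses the rating at treatment failure.

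For the primary outcome, SAP 3.2.2 deals with the within-"subject responses between the two eyes; an exchangeable working correlation structure will be" used, and adds sandwich standard errors. SAP 3.3.2 extends that method by outcome type: "Treatment effect on secondary outcome variables for efficacy that are continuous will be" analysed the same way, followed by a list. The rating is not on the list. It has its own paragraph, in which "the VFRC (improved, no change, worse) will be assessed via a logistic regression model" of the proportional-odds type, with a likelihood-ratio test and 98.3% intervals for the pairwise odds ratios. The closing paragraph of SAP 3.3.2 adds baseline PMD as covariate and nothing on clustering.

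Protocol 9.4 has the same structure. Its sentence on other aspects of the primary analysis gives baseline adjustment, interactions and model assumptions as examples. Between-eye correlation is not among them.

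On the unit of analysis, the outcome list in SAP 3.3.1 ends with "Data from all eligible eyes will be included in the analysis", and the entry for this rating says "All available visual field examinations will be analyzed".

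**The concern.** An ordinary proportional-odds fit and its likelihood-ratio test assume independent observations. Treatment is randomised by subject, so both eyes of a two-eyed subject sit in the same arm. If their ratings are positively correlated, the model counts more information than there is. Standard errors come out too small, p-values too small and odds-ratio intervals too narrow.

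The plan takes care of this elsewhere. PMD, papilledema grade, the OCT measures and acuity all get the GEE. For most subject-level outcomes the SAP notes that no working correlation structure is needed. The visual field rating gets neither treatment. At stake is the credibility of any pairwise claim on this rating and on its supplemental version.

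**Working it through.** **Inputs from the documents**
- Share of subjects with a second eligible eye: about 40% (SAP 2.0, Protocol 9.10).
- Between-eye correlation of the PMD outcome: 0.82 (same sections).
- Nominal level: 98.3% intervals, that is 5%/3 = 1.67% two-sided, z = 2.394. The SAP states no separate test level for this rating.

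**Assumed, because the documents do not give them**
- Between-eye correlation of the three-level rating. I cut a bivariate normal with latent correlation 0.5 to 0.82 into three levels.
- Category mixes (worse/same/improved, %): 10/20/70, 20/30/50, equal thirds, 5/15/80, 10/40/50, 5/35/60.

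**The plan's own figure.** The documents give no error rate for this rating, so the only figure to reproduce is the sample size. At α = 0.05/3, n = 2(2.394 + 1.175)² × (6.5/4.5)² ≈ 53.2, so 54 per group. Then 54/0.9 = 60. Both agree with the plan.

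**Analytic step.** With a share p of two-eyed subjects and rating correlation r, the true variance relative to the one the model assumes is

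ratio = [(1 − p) + p(2 + 2r)] / (1 + p) = [0.6 + 0.4(2 + 2r)] / 1.4 = 1 + r × 0.8/1.4,

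and the actual α is 2[1 − Φ(2.394/√ratio)]. For r = 0.50 the ratio is 1.286, 2.394/1.134 = 2.11, and α = 3.5%.

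| Latent correlation | Rating correlation r | Variance ratio | Actual α |
|---|---|---|---|
| 0.5 | 0.31–0.41 | 1.18–1.23 | 2.7–3.1% |
| 0.6 | 0.39–0.50 | 1.22–1.29 | 3.0–3.5% |
| 0.7 | 0.48–0.59 | 1.27–1.34 | 3.4–3.8% |
| 0.82 | 0.61–0.71 | 1.35–1.41 | 3.9–4.4% |
| (rating itself at 0.82) | 0.82 | 1.47 | 4.8% |

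The true standard error is therefore √1.18 = 1.09 to √1.41 = 1.19 times the reported one.

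**Simulation of the test as written.** Proportional odds with group and baseline PMD, no true effects, 60 subjects per group, 40% with two eyes, 5,000 runs per setting, Monte Carlo error at most 0.3 points:

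| Latent correlation | Likelihood-ratio test, mix 10/20/70 | Likelihood-ratio test, mix 20/30/50 | Clustered sandwich Wald, same data |
|---|---|---|---|
| 0.5 | 3.1% | 2.8% | 1.8%, 1.7% |
| 0.6 | 3.1% | 3.7% | 1.6%, 1.8% |
| 0.82 | 4.3% | 4.4% | 1.6%, 1.6% |

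Unclustered 98.3% intervals covered 95.7–97.3%.

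**Second simulation.** 54 subjects per group, mix 15/25/60, 10,000 trials with three pairs each. The likelihood-ratio test rejected in 3.2%, 4.0% and 4.4% at residual latent correlation 0.5, 0.7 and 0.82. Controls gave 1.9% with one eye per subject and 1.8% with two independent eyes, so almost all of the excess comes from clustering. Subject-clustered Wald tests gave 1.8% at all three correlations.

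**Sensitivity.**
- Two-eyed share 30% or 50% at r = 0.5: 3.1% or 3.8% (analytic).
- Latent correlation 0.3: 2.5% (simulated).
- 25% two-eyed at latent 0.7: 3.4% (simulated).
- 60% two-eyed at latent 0.82: 5.2% (simulated).

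The ratio does not depend on sample size. Leaving missing ratings unimputed (SAP 3.3.6) matters only if it changes the two-eyed share.

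**The case against.** **The unit is not stated.** This is the strongest objection, and it is correct. The sentence on all eligible eyes closes a list that also holds CSF pressure, SF-36, HIT-6 and weight, so it cannot settle the unit alone. The line on available examinations could mean available-case use. "Two size V stimulus fields will be performed in each eye" (Protocol 2.4.1.1) describes screening, and "Visual field at follow-up (eligible eyes and non-eligible eyes, separately" in SAP 3.8 concerns tabulations. With one rating per subject the inflation disappears. Against that, the SAP names the best eligible eye when it wants a subject-level covariate (the Cox model, SAP 3.6.1). It does not do so here and gives no rule for combining two eyes. The eye remains the natural reading, and under the other reading a rule is missing.

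**The size rests on assumptions.** This stands. The 0.82 is for the PMD outcome in a chart review with a different entry cut-off, and the floor of 0.5 is a choice. Correlation may also differ in the ONSF arm, where the eyes are operated on in sequence. The lowest results in the main range are 2.7–2.8%, slightly under 3%.

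**Importance.** Protocol 1.4.2 places the rating among other efficacy variables, although the Protocol Summary calls it key secondary. The primary analysis and the Month 6 PMD change already use the GEE, so no main conclusion moves. This limits the severity but does not make the stated test valid.

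**Scope.** Protocol 9.4 also gives surgical failure a logistic model with likelihood-ratio tests, and its unit in two-eyed ONSF subjects is unclear. The SAP does not carry it as a modelled outcome in section 3.3, so in the SAP the problem is confined to this rating and its supplemental version.

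**Alternative remedy.** A proportional-odds model with a subject random intercept would keep the likelihood-ratio test. Its odds ratio is subject-specific, however, unlike the population-averaged effect in the primary analysis.

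**Conclusion.** The concern holds. No between-eye method is stated for this rating, and the method that is stated is wrong if eyes are the unit. On that reading, with 40% of subjects contributing two eyes and a latent correlation of 0.5 to 0.82, each pairwise test runs at about 3–4.5% against 1.67%, roughly two to two and a half times nominal. The 98.3% intervals cover about 95.5–97%. A weaker correlation would shrink the excess, and a larger two-eyed share would increase it. This should be fixed, but it does not touch the primary result.

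**What to change.** State the unit of the rating first. If it is the eye, replace the likelihood-ratio sentence in SAP 3.3.2 with:

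> The VFRC rating will be analysed by eye with a cumulative-logit (proportional-odds) GEE, eyes clustered within subject, independence working structure, with treatment group and baseline PMD as covariates; pairwise Wald tests at 1.7% and 98.3% CIs will use sandwich standard errors.

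Use the same model for the supplemental version at treatment failure, and align Protocol 9.4 for this rating. If one rating per subject is intended, say so and give the rule for combining two eyes.

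The cost is one sentence in each document and no new data. Intervals become about 9–19% wider on the log-odds scale than the unclustered ones. The likelihood-ratio test is given up, because a GEE has no likelihood.
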